7.5.5.1 Capillary Leak Syndrome and Associated Symptoms

CLS is associated with vascular endothelial injury related to fusion protein administration and may occur 3 – 8 days after initiation of treatment.

Patients may exhibit symptoms of **hypotension**, fluid overload, evidenced by **weight gain** or edema, nausea, and anorexia, shortness of breath and, at times, confusion and muscle injury. Findings may include **hypoalbuminemia**, reductions in blood oxygen saturation, and evidence of pulmonary edema on chest x-ray. **These symptoms may present individually or as part of CLS.**

Refer to Section [7.5.5.1.1](#), Section [7.5.5.1.2](#), and Section [7.5.5.1.3](#) for the management of the individual symptoms of hypotension, increase in body weight, and hypoalbuminemia. If the constellation of symptoms is considered to be potentially representative of CLS, the patient is to be managed as described in Section [7.5.5.1.4](#).

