7.5.5.1.3 Hypoalbuminemia

Patients are to have serum albumin measurements performed daily until completion of SL-401 administration.

- In settings in which albumin is reduced to 3.0-3.5 g/dL (30-35 g/L) or by ≥ 0.5 g/dL (5 g/L) below the level at the start of the cycle, withhold SL-401 infusion and administer albumin 25 g IV daily or every 12 hours as clinically feasible until serum albumin is both ≥ 3.5 g/dL and not reduced by ≥ 0.5 g/dL from the level at the start of the cycle prior to resuming treatment with SL-401 in the same cycle.
- In settings in which albumin is reduced to <3.0 g/dL (30 g/L) or by more than 1.0 g/dL (10 g/L) below the level at the start of the cycle (i.e., from 4.3 g/dL to 3.2 g/dL), withhold SL-401 infusions for the duration of that particular cycle. Albumin should be administered until the albumin level is at least above 3.5g/dL. Consultation with the medical monitor is advised.
- Dosing in the next cycle may resume if albumin remains at 3.5 g/dL without additional albumin infusions.

Albumin infusions are supportive measures, and are not intended to enable treatment in settings in which hypoalbuminemia would otherwise preclude SL-401 administration.

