7.5.5.1.4 Capillary Leak Syndrome

Withhold SL-401 infusion for patients with clinical signs and symptoms consistent with CLS.

If CLS is identified, 1 mg/kg/day of methylprednisolone (or an equivalent) should be administered until resolution or as clinically indicated along with administration of albumin as specified in [Appendix E](#).

Ongoing CLS or CLS with clinical/hemodynamic instability

SL-401 administration during the cycle may not resume if there are signs or symptoms of CLS along with evidence of hemodynamic instability, significant clinical deterioration or changes in albumin, defined as a decrease to <3.0 g/dL or reduction by >1.0 g/dL from the start of the cycle or CLS elements have not resolved.

SL-401 administration may only resume in the next cycle if all CLS elements have resolved, and the patient is hemodynamically stable and laboratory values have recovered to a level that permits dosing.

CLS without clinical/ hemodynamic instability

In the setting of signs/symptoms of CLS that DID NOT include hemodynamic instability OR significant clinical deterioration OR reductions in albumin that would prevent further dosing, SL-401 administration in that cycle may be delayed and resume if there is no evidence of ongoing CLS, pending discussion with the study Medical Monitor.

Any subsequent SL-401 is to be administered on days *subsequent* to the identification of the abnormality (not the same day). If dosing is resumed, any subsequent doses in that cycle must be administered within the first 10 days of that cycle. SL-401 administration in subsequent cycles may resume per the normal schedule after Day 28 of the previous cycle.

Also see [Appendix E](#) for summary of recommended actions.

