15.5 Appendix E. CLS Management Guidance

CLS Element	Time of Presentation	Recommended Action	SL-401 Dosing Management
Serum albumin <3.2 g/dL (without albumin supplementation)	Prior to 1 st SL-401 administration	Do not dose (patient not eligible for participation)	
Serum albumin <3.5 g/dL OR reduced by ≥0.5 g/dL from pre-dose value (with or without albumin supplementation) A pre-dose body weight that is increased by ≥1.5 kg over the previous day's pre-dose weight	During SL-401 dosing ¹	
 • For the CLS element of albumin decrease: 
 ▪ Administer albumin 25 g IV (q12h or more frequently as practical) until serum albumin is both ≥3.5 g/dL and not reduced by ≥0.5 g/dL from pre-dose value • For the CLS element of body weight increase: 
 ▪ Administer albumin 25 g IV (q12h or more frequently as practical), and manage fluids and blood pressure, as clinically indicated, until body weight increase has resolved (i.e. the increase is no longer greater than 1.5 kg from the previous day's pre-dose weight) 	
 • Hold SL-401 dosing until the relevant CLS element has resolved as specified by Recommended action²
Edema, fluid overload and/or hypotension		
 • Administer albumin 25 g IV (q12h, or more frequently as practical) until serum albumin is ≥3.5 g/dL • Administer 1 mg/kg of methylprednisolone (or an equivalent) per day, until resolution of CLS element or as clinically indicated • Aggressive management of fluids status, which could include intravenous fluids and/or diuretics, until resolution of CLS element or as clinically indicated 	

1. For patients eligible for treatment with SL-401 with serum albumin >3.2 g/dL but <3.5 g/dL on the day of dosing, IV albumin (25 g) is recommended prior to administration of SL-401 to increase the serum albumin to ≥3.5 g/dL before the 1st dose of SL-401.
2. SL-401 administration may resume in the same cycle if all CLS elements have resolved and the patient did not require measures to treat hemodynamic instability. SL-401 administration should be held for the remainder of the cycle if CLS elements have not resolved or the patient required measures to treat hemodynamic instability (even if resolved), and SL-401 administration may only resume in the next cycle if all CLS elements have resolved, and the patient is hemodynamically stable.

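### Appendix E drops the cycle-ending albumin limit of section 7.5.5.1.3 and permits same-cycle re-dosing that the section forbids

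*Protocol*

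**What the plan says.** Protocol 7.5.5.1 sends readers to sections 7.5.5.1.1 to 7.5.5.1.3 "for the management of the individual symptoms of hypotension, increase in body weight, and hypoalbuminemia".

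Section 7.5.5.1.3 has two tiers:

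- **Lower tier:** albumin of 3.0-3.5 g/dL, or a fall of at least 0.5 g/dL since the cycle began. Dosing is held and may resume in the same cycle after correction.
- **Upper tier:** albumin below 3.0 g/dL, or a fall of more than 1.0 g/dL. Here the instruction is to "withhold SL-401 infusions for the duration of that particular cycle". The section illustrates this with a fall from 4.3 to 3.2 g/dL. It closes by saying that albumin infusions "are not intended to enable treatment in settings in which hypoalbuminemia would otherwise preclude SL-401 administration".

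Section 7.5.5.1.4 uses the same limit when signs or symptoms of CLS are present. Same-cycle dosing is barred for "changes in albumin, defined as a decrease to <3.0 g/dL or reduction by >1.0 g/dL from the start of the cycle". It then refers to Appendix E "for summary of recommended actions".

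Appendix E has one albumin row for the dosing period: below 3.5 g/dL, or "reduced by ≥0.5 g/dL from pre-dose value". The action is to give albumin and hold SL-401 until corrected. Footnote 2 then says: "SL-401 administration may resume in the same cycle if all CLS elements have resolved and the patient did not require measures to treat hemodynamic instability". It also says: "SL-401 administration should be held for the remainder of the cycle if CLS elements have not resolved or the patient required measures" for hemodynamic instability. Neither the 3.0 g/dL floor nor the 1.0 g/dL fall appears anywhere in the appendix.

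**The concern.** This is more than a shortened summary. The appendix's albumin row has no lower bound, so it also covers the severe values that the body handles separately. Footnote 2 sets its own criteria for resuming and for ending the cycle, and depth of the albumin fall is in neither. A site working from the table could bring albumin back with IV albumin and re-dose a hemodynamically stable patient in a cycle that section 7.5.5.1.3 had ended.

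The reference level is a second mismatch. The body measures the fall from the albumin at the start of the cycle. The appendix says *pre-dose value*, and the weight criterion beside it uses the previous day's pre-dose weight. The albumin term can be read either way.

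CLS was the principal DLT in Study 50047, though relatively uncommon at or below the MTD (Protocol 3.6.3). Safety characterization is a primary objective. SAP 2.2 lists all protocol violations, and the conflict leaves it unclear whether re-dosing after such a fall is one.

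**Working it through.** There is no statistical figure to reproduce. The check applies both rules to the same cases and then bounds the extra drug.

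**1. Same patient, two rules** (*pre-dose value* read as the level at the start of the cycle)

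| Start to low (g/dL) | Fall | Section 7.5.5.1.3 | Appendix E |
|---|---|---|---|
| 4.3 to 3.2 | 1.1 | 1.1 > 1.0: cycle ends | 3.2 < 3.5 and 1.1 ≥ 0.5: hold, resume above 3.8 |
| 3.6 to 2.9 | 0.7 | 2.9 < 3.0: cycle ends | 2.9 < 3.5: hold, resume at 3.5 or more (then down only 0.1) |
| 4.0 to 3.3 | 0.7 | lower tier: hold, may resume | hold, may resume |

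The rules agree in the lower tier and part exactly at the upper-tier limit.

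**2. Effect of the reference level**

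Under Appendix E, albumin must be at least 3.5 g/dL and down by less than 0.5 g/dL from the reference. For the 4.3 to 3.2 example:

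- Reference = start of cycle (4.3): 4.3 − 0.5 = 3.8, so resume above 3.8 g/dL.
- Reference = level before the last infusion given. Assume this was 3.9 to 4.3, values that would not themselves have triggered a hold. For 3.9, resume at 3.5. For 4.0, above 3.5. For 4.1, above 3.6. For 4.2, above 3.7. For 4.3, above 3.8.

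The threshold therefore lies between 3.5 and just above 3.8 g/dL, depending on the reading.

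**3. Ceiling on extra infusions**

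Inputs: five daily infusions, all within the first 10 days of the cycle (Protocol 7.5.2, 7.5.5), and a Stage 2 dose of 12 µg/kg/day (SAP 1.2.1). Assumptions: the course was uninterrupted until the limit was met before the infusion on Day d, and dosing resumes on a later Day r.

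- Given before the event: d − 1. The body stops here.
- Infusions left: 5 − (d − 1) = 6 − d.
- Days available from r to 10: 11 − r.
- Extra under Appendix E = min(6 − d, 11 − r).

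| Limit met before infusion on | Extra infusions by day of resumption | Extra dose (× 12 µg/kg) |
|---|---|---|
| Day 2 | 4 (Days 3-7), 3 (Day 8), 2 (Day 9), 1 (Day 10) | 48 to 12 µg/kg |
| Day 3 | 3 (Days 4-8), 2 (Day 9), 1 (Day 10) | 36 to 12 µg/kg |
| Day 4 | 2 (Days 5-9), 1 (Day 10) | 24 to 12 µg/kg |
| Day 5 | 1 (Days 6-10) | 12 µg/kg |

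The extra is 0 if dosing is not resumed by Day 10, if the fall comes after infusion 5, or if the site follows section 7.5.5.1.3.

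**The case against.** The case for leaving this alone is that the body plainly governs.

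- Sections 7.5.5.1 and 7.5.5.9 both route albumin questions to 7.5.5.1.3, and section 8.8 refers to it for giving albumin. Section 7.5.5.1.3 never mentions Appendix E.
- Elsewhere the body cites the appendix for giving albumin or as a summary, never for the decision to resume. The appendix is titled guidance and is permissive, so a site can satisfy both texts by following the stricter one.
- Section 7.5.5.1.3 advises consulting the medical monitor at this tier. Section 7.5.5.1.4 makes same-cycle dosing after CLS signs subject to discussion with the Medical Monitor.
- The SAP already connects albumin events with dosing in part. Hypoalbuminaemia terms belong to the CLS events of special interest (SAP 4.4.2), and exposure before CLS onset is summarized (SAP 4.4.2.1).
- In Study 50047 albumin was lowest about one week after the first infusion (Protocol 3.6.1), so many falls would come after infusion 5. Enrollment was also complete enough to be reported at database lock.

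Most of this stands. It shows which rule was meant, and that the practical effect is probably limited. It does not remove the conflict. None of these texts states precedence, and footnote 2 is an express permission, not a silence. The medical monitor advice at this tier is not carried into the appendix. Exposure before CLS onset does not show whether a patient was dosed again after meeting the limit. Clear intent is a reason to correct the appendix.

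**Conclusion.** The concern holds. Appendix E omits the limit of below 3.0 g/dL or a fall of more than 1.0 g/dL, and footnote 2 permits same-cycle dosing after such a fall once it is corrected. The divergence at the 3.0 g/dL floor does not depend on how *pre-dose value* is read. The body is probably the intended rule, but this is inferred from routing and wording.

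The excess is at most 4 infusions (48 µg/kg at 12 µg/kg/day) in one cycle, and zero in many cases. That ceiling assumes an uninterrupted course, no treatment for hemodynamic instability, correction in time, and a site working from the appendix. The documents do not give the share of patients who would meet the limit during dosing. No endpoint, sample size or test is affected. It is a safety stopping rule stated in two incompatible ways, and it should be fixed.

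**What to change.** **Protocol**

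- Add a row to Appendix E, and a clause to footnote 2: albumin below 3.0 g/dL, or more than 1.0 g/dL under the cycle-start level, ends SL-401 for that cycle even if later corrected.
- In the albumin row, replace *pre-dose value* with the cycle-start level used in section 7.5.5.1.3.
- State that sections 7.5.5.1.3 and 7.5.5.1.4 govern wherever Appendix E differs.

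**SAP (optional)**

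- Derive a flag for any patient dosed again in a cycle after meeting the 7.5.5.1.3 limit, using that cycle's Day 1 albumin. The exposure and laboratory data are already planned for listing (SAP 4.4.1, 4.4.3).

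The cost is one row, one clause, one term and one sentence in the protocol. The flag is one derived variable for 18 + 9 = 27 patients (SAP 3.1). No new data or patients are needed. Rewording cannot change exposure already given, so for this trial the flag is the part that can still tell the reader whether such re-dosing occurred.

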7.5.5.1.4 Capillary Leak Syndrome

Withhold SL-401 infusion for patients with clinical signs and symptoms consistent with CLS.

If CLS is identified, 1 mg/kg/day of methylprednisolone (or an equivalent) should be administered until resolution or as clinically indicated along with administration of albumin as specified in [Appendix E](#).

Ongoing CLS or CLS with clinical/hemodynamic instability

SL-401 administration during the cycle may not resume if there are signs or symptoms of CLS along with evidence of hemodynamic instability, significant clinical deterioration or changes in albumin, defined as a decrease to <3.0 g/dL or reduction by >1.0 g/dL from the start of the cycle or CLS elements have not resolved.

SL-401 administration may only resume in the next cycle if all CLS elements have resolved, and the patient is hemodynamically stable and laboratory values have recovered to a level that permits dosing.

CLS without clinical/ hemodynamic instability

In the setting of signs/symptoms of CLS that DID NOT include hemodynamic instability OR significant clinical deterioration OR reductions in albumin that would prevent further dosing, SL-401 administration in that cycle may be delayed and resume if there is no evidence of ongoing CLS, pending discussion with the study Medical Monitor.

Any subsequent SL-401 is to be administered on days *subsequent* to the identification of the abnormality (not the same day). If dosing is resumed, any subsequent doses in that cycle must be administered within the first 10 days of that cycle. SL-401 administration in subsequent cycles may resume per the normal schedule after Day 28 of the previous cycle.

Also see [Appendix E](#) for summary of recommended actions.

7.5.5.2 Chills, Anaphylaxis, and Hypersensitivity Reactions

Withhold SL-401 infusion for chills, anaphylaxis and hypersensitivity reactions.

Chills associated with SL-401 administration may be treated with meperidine 12.5-50 mg IV or morphine sulphate 1-2 mg IV (or equivalent doses of other opiates). Anaphylaxis and hypersensitivity reactions associated with rash, fever, urticaria, bronchospasm, and/or angioedema will be treated with 100 mg IV methylprednisolone (or an equivalent corticosteroid) and 25-50 mg IV diphenhydramine (or equivalent H1-histamine antagonist). More severe symptoms will also be treated with 0.3 mL epinephrine (1:1000) IV once. Patients with anaphylactic (Grade 4) reactions or Grade ≥ 3 hypersensitivity reactions should not receive additional infusions of SL-401.

In the setting of Grade 1-2 hypersensitivity reactions, administration of subsequent SL-401 may be attempted provided that any systemic symptoms of the prior Grade 1-2 hypersensitivity reaction resolved within 24 hours with appropriate supportive measures. Premedication for patients with prior Grade 1-2 hypersensitivity reactions should include the agents specified in Section [7.5.3](#); additional premedication may be provided at the Investigator's discretion and should be discussed with the Medical Monitor or designee. Please consult Section [10.7](#) concerning recommended optimal reporting of SL-401-related hypersensitivity reactions.

Blood (serum) samples (10 mL, for immunogenicity) will be collected anytime during the study when clinical manifestations are observed suggesting either an infusion related reaction or drug hypersensitivity.

7.5.5.3 Transaminase (AST/ALT) Elevations

In settings in which transaminases (AST/ALT) are elevated to $>5 \times$ ULN, no subsequent SL-401 will be administered for the duration of the cycle.

7.5.5.4 Body Temperature $\geq 38^{\circ}\text{C}$

For temperature $\geq 38^{\circ}\text{C}$, draw blood culture $\times 2$, and collect urine for urinalysis, as clinically indicated. SL-401 may be administered pending resolution, provided that an appropriate evaluation for infectious etiologies has been undertaken, and provided that the Investigator determines that there is minimal likelihood of uncontrolled systemic infection including sepsis; this may occur on the same day as the temperature elevation, or on subsequent days.

7.5.5.5 Serum Creatinine $>1.8 \text{ mg/dL (159 } \mu\text{mol/L)}$

Withhold SL-401 infusion until serum creatinine resolves to $\leq 1.8 \text{ mg/dL (159 } \mu\text{mol/L)}$. Dosing may resume upon recovery of serum creatinine if this occurs within the first 10 days of a cycle.

7.5.5.6 Tachycardia, Bradycardia, or Hypertension

Withhold SL-401 infusion for patients with a heart rate ≥ 130 or heart rate ≤ 40 bpm or systolic BP ≥ 160 mmHg until resolution.

7.5.5.7 Tumor Lysis Syndrome

Treatment with cytotoxic cancer therapies in the setting of high tumor burden may cause rapid tumor lysis syndrome (TLS) and associated electrolyte and renal disturbances. A low incidence of TLS has been reported with SL-401. The Sponsor advises continued awareness of the possibility of acute and potentially life-threatening TLS in patients with high disease burden.

Serum chemistries to monitor TLS are included in the daily laboratory tests during SL-401 infusion (e.g., creatinine, potassium, phosphorus, uric acid, LDH). In the event of evidence of TLS, local standards should be followed to monitor and treat TLS. For example, IV hydration in addition to other measures to maintain urine output, hypouricemic agents, and additional interventions to correct electrolyte abnormalities may be given at the discretion of the Investigator.

7.5.5.8 Cytokine Release Syndrome

Cytokine release syndrome results from an excessive immune response with elevated circulating cytokines that can cause symptoms ranging from flu-like symptoms, confusion, and rigors to a potentially fatal sepsis syndrome with circulatory collapse. The Sponsor recommends vigilance and appropriate clinical management that may include, hydration, steroids, and/or anti-IL-6 agents at the investigator's discretion.

7.5.5.9 Other Toxicities

Hold dose for clinically significant Grade 3/4 toxicities for the current cycle, with the exception of the following Grade 3 toxicities, if deemed appropriate by the Investigator:

- Arthralgia
- Myalgia
- Fever responding to treatment with no active infection
- Nausea and/or vomiting, or diarrhea associated with suboptimal prophylaxis and/or treatment
- Reversible clinical chemistry abnormalities (refer to Sections [7.5.5.1.3](#), [7.5.5.3](#), and [7.5.5.5](#) for details regarding albumin, liver transaminases, and creatinine).

Refer to Section [7.5.5.10.1](#) for further instruction regarding dose delay and reduction.

7.5.5.10 Dose Modifications/Delays and Management Procedures for Other Toxicities Associated with SL-401

7.5.5.10.1 Nonhematological Toxicity

Table 3 summarizes the dose modification guidelines for SL-401-related nonhematological toxicities (other than those identified in Section [7.5.5.1](#) through Section [7.5.5.8](#)).

Table 3: Dose Delays/Modifications for Other SL-401-Related Nonhematological Toxicity

CTCAE Grade	SL-401 Dose Adjustment/Delays
Any Grade 1-2 toxicities	
 • No dose adjustment or delay
Grade 3 with resolution to Grade ≤ 1 or baseline by Day 28 of cycle	
 • No dose adjustment or delay
Grade 3 without resolution to Grade ≤ 1 or baseline by Day 28 of cycle	
 • Delay the start subsequent cycle by up to 14 days (i.e., up to 42 days since the first dose in the previous cycle). 
 – If after 14 days the toxicity resolves to Grade ≤ 1 or baseline, no dose adjustment required and the cycle may start. – If after 14 days the toxicity has not resolved, monitor weekly until resolution; discuss additional dosing and schedule with the Medical Monitor.
Grade 4 (excluding transient [≤ 14 days] asymptomatic transaminase or CPK elevations) with resolution to Grade ≤ 1 or baseline by Day 28 of cycle	
 • Reduce dose for subsequent cycle (see Section 7.5.5.11) and the cycle may start.

CTCAE Grade	SL-401 Dose Adjustment/Delays
Grade 4 without resolution to Grade ≤ 1 or baseline by Day 28 of cycle	
 Delay the start subsequent cycle by up to 14 days (i.e., up to 42 days since the first dose in the previous cycle). If after 14 days the toxicity resolves to Grade ≤ 1 or baseline, resume dosing at a reduced dose (see Section 7.5.5.11). If after 14 days the toxicity has not resolved, monitor weekly until resolution; discuss additional dosing and schedule with the Medical Monitor

Note that delays in start of subsequent cycles greater than 3 weeks (6 weeks following the start of the prior treatment cycle) will be acceptable only after discussion with the Medical Monitor regarding the potential risk/benefit of further treatment.

7.5.5.10.2 Hematological Toxicity

Patients with neutropenia or thrombocytopenia as a consequence of their disease do not require treatment interruptions for myelosuppression. Dose-modifications in these patients should be considered on a case-by-case basis and discussed with the Medical Monitor. The following guidelines can be used for these patients:

- Patients with a response and pre-cycle counts of neutrophils $>1000/\mu\text{L}$ and platelets $>50,000/\mu\text{L}$ who have sustained low counts of neutrophils $<500/\mu\text{L}$ and/or platelets $<20,000/\mu\text{L}$ for more than 2 consecutive weeks in the current cycle, may receive a subsequent cycle of SL-401 at a reduced dose, at the Investigator's discretion.
- If there are persistent blasts in the peripheral blood or $>5\%$ blasts in the bone marrow, continue treatment regardless of neutrophil and platelet count and give supportive care as needed.
- If no evidence of leukemia in the bone marrow, consider holding (postponing) therapy until recovery of neutrophils to $\geq 1000/\mu\text{L}$ and platelets $\geq 50,000/\mu\text{L}$, then resume SL-401 at the same or reduced dose according to guidelines mentioned above.

